## LIST OF ABBREVIATIONS

AE	Adverse Event
BM	Bowel Movement
CBC	Complete Blood Count
CEA	Carcinoembryonic Antigen
CRS	Cytoreductive Surgery
CTCAE	Common Terminology Criteria for Adverse Events
DSMB	Data and Safety Monitoring Board
ECOG	Eastern Cooperative Oncology Group
GI	Gastrointestinal
HIPEC	Hyperthermic Intraperitoneal Chemotherapy
HRPP	Human Research Protections Program
IRB	Institutional Review Board
LN	Lymph Node
NCI	National Cancer Institute
OS	Overall Survival
PC	Peritoneal Carcinomatosis
PD	Progressive Disease
PFS	Progression Free Survival
PO	Per Os (By Mouth)
POD	Postoperative Day
RCT	Randomized Controlled Trial
SAE	Serious Adverse Event
UPR	Unanticipated Problems involving Risk to subjects or others

**STUDY SCHEMA**

**NOTE: Randomized Patients who do not undergo CRS/HIPEC will be considered screen failures after randomization.**

## STUDY SUMMARY

Title	The ILEUS Study: A Phase 2 Randomized Controlled Trial Investigating Alvimopan for Enhanced Gastrointestinal Recovery after Cytoreductive Surgery and Hyperthermic Intraperitoneal Chemotherapy
Short Title	Phase 2 Randomized Controlled Trial of Alvimopan after CRS/HIPEC
Phase	II
Methodology	Double-blind, randomized, placebo-controlled trial
Study Duration	2 years
Study Center(s)	Single-center (UCSD)
Objectives	
Primary Endpoint
 
 
Time to recovery of upper and lower GI function (GI-2), as measured by the later of the following 2 events: time that the patient first tolerates solid food and time that the patient first passes bowel movement
 
 
Secondary Endpoints
 
 
Proportion of prolonged ileus (> 7 days)
 
Time to return of bowel function components: time to first flatus, time to first bowel movement, time to tolerance of solid food
 
Time to hospital discharge order written
 
Adverse events
 
Subgroup analyses: number of anastomoses, number of visceral resections, epidural/no epidural, etc.
 

Number of Subjects	128
Diagnosis and Main Inclusion Criteria	Eligible participants are those who undergo open cytoreductive surgery (CRS) and hyperthermic intraperitoneal chemotherapy (HIPEC)
Study Product(s), Dose, Route, Regimen	Alvimopan 12 mg, by mouth, 30 minutes to 5 hours preoperatively, then POD 1 by mouth twice for the earlier of 7 days or hospital discharge (maximum 15 doses)
Duration of administration	8 days (maximum)
Reference therapy	Placebo
Statistical Methodology	Based upon a sample size of n=64 patients per group (128 total), this study has 82% power to detect a HR of 1.59 which approximately corresponds to an improvement in the median primary endpoint (GI-2) from 9 days to 5.7 days, with a single-sided alpha of 0.05, and 5% withdrawal rate.

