**9.2 Sample Size and Accrual**

Our sample size calculation is based on detecting a difference in distributions of times until GI-2 between groups. Assuming a similar hazard ratio between the Alvimopan 12 mg and placebo groups as Xu et. al. (HR = 1.59, which approximately corresponds to an improvement in the median primary endpoint (GI-2) from 9 days to 5.7 days), a log-rank test for a difference in distributions of times until GI-2 is met will have 80% power at the one sided 0.05 significance level with a total sample size of n = 122. (Note that this does not adjust for a reduction in power due to the interim analysis.) Accounting for a 5% drop-out rate, the total enrolled sample size is 128 participants.

Approximately 60-70 CRS/HIPEC procedures are performed at UCSD annually. Accrual of 128 participants could occur over 2-3 years. Annual target accrual will be 40 participants per year.

Accrual Targets			
Ethnic Category	Sex/Gender		
	Females	Males	Total
Hispanic or Latino	8	5	13
Not Hispanic or Latino	63	52	115
Ethnic Category: Total of all subjects	71	57	128
Racial Category			
American Indian or Alaskan Native	0	0	0
Asian	8	5	13
Black or African American	2	1	3
Native Hawaiian or other Pacific Islander	1	1	2
White	60	50	110
Racial Category: Total of all subjects	71	57	128

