### **9.8 Interim analysis**

When the 64th subject has reached the primary endpoint (or been censored because of loss to follow-up), a futility analysis will be performed.

The futility analysis will use a stochastic curtailment approach (Crowley and Anhkerst, Clinical Trials in Oncology, 2nd ed p 233), as computed in PASS 14.0.6. If at the interim analysis, the conditional power (i.e. the probability that the study will go on to reject the null hypothesis, given the observed data at the interim analysis) is below 20%, the study will stop. This futility analysis will be carried out by the statisticians at the MCC Biostatistics Shared Resource, using a one-sided logrank test at the 5% significance level.

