## 2. Protocol Synopsis

Planned Accrual: N= 128; approximately 60-70 CRS/HIPEC procedures are performed annually at UCSD.

Study Design: The proposed study is a prospective, randomized controlled phase 2 trial. Subjects will be assigned to either placebo or alvimopan groups according to a block randomization.

Primary Objective: To determine the efficacy of alvimopan to reduce postoperative ileus in patients undergoing CRS/HIPEC, as measured by the composite of time to recovery of upper and lower GI function.

Treatment Description: Alvimopan (12 mg) or Placebo 30 minutes – 5 hours prior to surgery, then twice daily (BID) starting POD 1 for a maximum of 7 days or until hospital discharge.

Primary Endpoint(s): Time to either 1st solid food or 1st bowel movement postoperatively, whichever is later.

Study Stopping Rules:

At accrual of 64 patients, a futility analysis will be performed. If the conditional power (as computed for log-rank tests) is less than 10% at this halfway point, we will suspend the study. The conditional power threshold of 10% was chosen based on boundaries set in Jennison and Turnbull, as well as with consideration to the probability of stopping early based on a series of effect sizes. If the null hypothesis is true (i.e. a hazard ratio of 1), the study will stop early at the interim to fail to reject the null hypothesis 69.49% of the time. Under the alternative hypothesis, the study will stop early 10.35% of the time while maintaining a type II error rate of 20%.

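### The synopsis power of 82% leaves out the futility stop without saying so, and Appendix C's claim that type II error stays at 20% conflicts with its own stop probabilities

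*Combined protocol and SAP*

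**What the plan says.** Four places bear on the power of one design.

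- **Study Summary, Statistical Methodology:** for 64 per group, "this study has 82% power to detect a HR of 1.59", "with a single-sided alpha of 0.05, and 5% withdrawal rate". The interim analysis is not mentioned.
- **Section 9.2:** for the same hazard ratio, the log-rank test "will have 80% power at the one sided 0.05 significance level with a total sample size of n = 122", inflated for 5% drop-out to 128. It adds: "Note that this does not adjust for a reduction in power due to the interim analysis".
- **Section 9.8:** a futility look once 64 subjects have reached the endpoint or been censored. If conditional power "is below 20%, the study will stop". The hazard ratio assumed for the data still to come is not given.
- **Appendix C, Protocol Synopsis:** a futility look at accrual of 64, with suspension if conditional power is under 10%. Under the null the study stops early 69.49% of the time. Under the alternative, "the study will stop early 10.35% of the time while maintaining a type II error rate of 20" per cent.

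**The concern.** A futility stop that is obeyed, with the final critical value unchanged, can only lower power: some trials that would have rejected at the end are stopped halfway. So 82% in the synopsis, 80% before the interim in section 9.2, and 80% after the interim in Appendix C do not sit together. The reader also meets two thresholds, 20% and 10%, with different costs in power.

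At stake is the chance of missing a true hazard ratio of 1.59. A reader of the synopsis would put it at 18%, and a reader of Appendix C at 20%. Type I error is not inflated, because a futility stop makes the test slightly conservative.

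**Working it through.** **Inputs.** HR 1.59, one-sided alpha 0.05 (critical value 1.645), 122 patients (section 9.2). For the synopsis, 128 × 0.95 = 121.6, so the same number is inferred. Interim at 64 patients: information fraction t between 0.50 (64/128) and 0.525 (64/122). Assumption: all 122 reach GI-2, since the documents give no event count.

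**Step 1: reproduce the stated powers, no interim.** Let θ be the expected final Z; power = Φ(θ − 1.645).

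- Schoenfeld: θ = √(122/4) × ln 1.59 = 5.523 × 0.4637 = 2.561; power Φ(0.916) = 82.0%.
- Freedman: θ = √122 × 0.59/2.59 = 2.516; power Φ(0.871) = 80.8%. For 80% this formula needs 120 events.

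Both stated figures are therefore fixed-design figures. The gap fits a choice of formula, or achieved against target power.

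**Step 2: find the method behind Appendix C.** Z1 has mean θ√t, Z2 has mean θ, and their correlation is √t. With threshold γ and z_γ its normal quantile, the study stops when Z1 is below:

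- current trend: √t × (1.645 + z_γ√(1−t))
- design HR: (1.645 + z_γ√(1−t) − θ(1−t)) / √t

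At t = 0.50 and γ = 10%, 1.645 − 1.2816 × 0.7071 = 0.739.

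| Method | Bound for Z1 | Stop under null | Stop under HR 1.59 |
|---|---|---|---|
| Appendix C, stated | – | 69.49% | 10.35% |
| Current trend | 0.522 | 69.9% | 9.9-10.4% |
| Design HR | −0.766 to −0.735 | 22-23% | 0.5-0.6% |

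Conditional power under the null hazard ratio does not fit either: the bound is 0.739/0.7071 = 1.045, so the null stop probability is 85%. Of the three, only current trend matches.

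**Step 3: test Appendix C on its own numbers.** The two stop probabilities fix the bound and θ at t = 0.50, whatever definition of conditional power lies behind them. The bound is Φ⁻¹(0.6949) = 0.510. Since Φ⁻¹(0.1035) = −1.262, θ = (0.510 + 1.262)/0.7071 ≈ 2.505. Fixed-design power is Φ(2.505 − 1.645) = 80.5%. Power with the stop, P(Z1 > 0.510 and Z2 > 1.645), is 77.2%. Type II error is therefore near 23%. The 20% figure agrees with the design before the stop, not after it.

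**Step 4: power with the stop, 122 events.** This is P(Z1 ≥ bound and Z2 > 1.645). Ranges run from t = 0.50 to t = 0.525.

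| Conditional power | Threshold | Schoenfeld | Freedman |
|---|---|---|---|
| Current trend | 10% (Appendix C) | 78.7-79.0% | 77.4-77.7% |
| Current trend | 20% (section 9.8) | 76.3-76.7% | 75.0-75.4% |
| Design HR | 10% | 82.0% | 80.8% |
| Design HR | 20% | 81.8% | 80.6% |

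A simulation of 100,000 log-rank trials (exponential times, no censoring) gave 80.9% with no interim, 77.5-77.6% for current trend at 10%, 75.1-75.3% for current trend at 20%, and 80.6-80.9% for the design HR.

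**The case against.** - **Neither 82% nor 80% is an arithmetic error.** A reader might infer one from the disagreement, but both reproduce, and two points between approximations is editorial. This stands in full.
- **Section 9.2 discloses the omission.** It never claims 80% net of the interim. This stands for section 9.2. It does not help the synopsis, which gives the higher figure without the caveat, or Appendix C, which claims the opposite.
- **The loss depends on a definition that section 9.8 does not give.** A reader might infer that delivered power is simply 75-77%, or that 80% is lost under both thresholds. The documents do not support that. Under the design hazard ratio, power stays at 80.6% or more at either threshold. Current trend is inferred from Appendix C's figures for a 10% rule, and carrying it over to the 20% rule is plausible but not documented. This stands, and it limits the size that can be claimed.
- **The final critical value could be lowered to use the alpha that a binding stop frees.** With Step 3's bound and θ, a critical value of 1.587 restores 5% and gives 78.5% power. With 122 events and the 10% current-trend rule, a value of about 1.585-1.588 gives 78.7-80.2%. That would bring Appendix C close to its claim, but no such adjustment is described: sections 9.5 and 9.8 both test at 5%.
- **Appendix C is a monitoring-report template and the error is 1-3 points.** True, but it is the only place that states the operating characteristics of the stop.

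**Conclusion.** The point holds in limited form. Appendix C's 20% type II error is wrong on its own numbers: the rule that fits them gives about 21-23%, that is, power of about 77-79%. The synopsis figure of 82% is a sound fixed-design figure presented as the power of a design that has a futility stop.

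Beyond that the size is conditional. Current-trend conditional power with the 20% threshold of section 9.8 gives about 75-77%, or roughly one miss in four at a true HR of 1.59. The design hazard ratio costs about 0.3 points or less.

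All figures assume a stop that is obeyed, an unchanged final critical value and 122 events. Section 2.3 censors patients discharged before GI-2 recovery. Any such censoring would lower every figure here, by an amount the documents do not allow one to compute.

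**What to change.** 1. Reconcile the 20% threshold of section 9.8 with the 10% threshold of Appendix C, and state one.
2. State in section 9.8 which hazard ratio is assumed for the remaining data when conditional power is computed.
3. Give one power figure, with the stop included, in the Study Summary, section 9.2 and Appendix C. Under current trend and 122 events this is about 75-77% for a 20% threshold or 77-79% for a 10% threshold; under the design HR it is 80.6-82.0%. Name the formula and the assumed number of events.
4. Delete the statement that type II error is held at 20%, or replace it with the value for the rule adopted.

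The cost is a text change only. Unless the design hazard ratio is adopted, the stated power becomes slightly less favourable.

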## **1.0 BACKGROUND AND RATIONALE**

---

### **1.1 Disease Background**

The peritoneum is a common site of metastasis, with approximately 55,000 new cases of peritoneal metastases occurring annually in the US. Tumors that commonly metastasize to the peritoneum include gastrointestinal (colorectal, small intestine, appendix, gastric, pancreatic, gallbladder, liver), gynecologic (ovarian), and primary peritoneal (peritoneal mesothelioma, primary peritoneal serous carcinoma) malignancies. Tumor histology and extent of disease are the primary determinants of long-term outcome, but patients with peritoneal metastases typically have a poor prognosis – 16 months median survival from colorectal cancer. Treatment options for peritoneal metastases are limited as systemic chemotherapy has poor penetration of the peritoneum and many peritoneal tumors are hypovascular and can be surrounded by a viscous layer of mucin. The fact that the peritoneal cavity may represent the only site of metastatic disease in selected patients has prompted the utilization of aggressive surgical resection (cytoreduction) and hyperthermic intraperitoneal chemotherapy (HIPEC) in the treatment of peritoneal metastases. HIPEC is a method of delivering high doses of cytotoxic chemotherapy directly to the peritoneal cavity with limited systemic toxicity, and is typically performed concurrently with surgical resection of visible intraperitoneal disease (cytoreductive surgery, CRS). The combined procedure (CRS/HIPEC) generally is performed through a large midline incision and includes extensive lysis of adhesions, resection of all visible peritoneal metastases, often with multivisceral resections including bowel resections and possibly multiple anastomoses, and requires a mean of eight hours of operative time. Large case series have estimated CRS/HIPEC doubles the median survival versus systemic chemotherapy alone in certain settings (colorectal cancer, appendiceal cancer and peritoneal mesothelioma). Perioperative complications of this extensive surgery are considerable, with a 1-2% risk of mortality and 16% risk of severe morbidity. This procedure remains highly specialized and is mostly performed in a limited number of high-volume centers in the US, which include UCSD. Approximately 60-70 CRS/HIPEC procedures are performed annually at UCSD.

The median length of stay after CRS/HIPEC is 10 days at our institution. A majority of the hospital stay is comprised of awaiting return of bowel function. The first flatus or bowel movement does not typically occur until postoperative day 4-5, and in 13% of patients it takes longer than 7 days. This is despite the fact that all patients undergo enhanced recovery pathways; including early mobilization, foley catheter removal as soon as feasible, and early advancement to liquid diet. Although attempts are made to minimize narcotic use after CRS/HIPEC - including use of epidural catheters and opioid-sparing medications (such as ketorolac and lidocaine patch) – all patients still require postoperative narcotics, which likely contributes to the prolonged ileus.

### **1.2 Study Agent**

Alvimopan is an oral peripherally-acting mu opioid receptor antagonist, with limited ability to cross the blood-brain barrier. There have been eight randomized-controlled trials published in English language journals documenting the safety and efficacy of alvimopan for postoperative ileus.

From a safety standpoint, a meta-analysis of all randomized controlled trials found the

most common adverse events with alvimopan included nausea, vomiting, constipation, flatulence, distension, headache, and pruritis (all greater than 10% in incidence). Rates of all common AEs from this meta-analysis is listed in the table below.

Adverse Event	Rate (%) 
Nausea	56.1
Vomiting	18.3
Constipation	15.4
Flatulence	14.5
Distension	12.2
Headache	11.2
Hypotension	8.5
Hypertension	9.4
Pyrexia	9.9
Pruritis	11.7
Tachycardia	7.1
 Among patients receiving 12 mg alvimopan dose	

It is worth noting that most of the GI-related adverse events are also symptoms of postoperative ileus, making attribution to alvimopan imprecise. Furthermore, many AEs were significantly lower in the alvimopan groups than the placebo groups (nausea, vomiting, constipation, and pyrexia). The remaining common AEs were no different in the alvimopan and placebo groups.

Serious adverse events were reported in 3-25.7% of participants in RCTs, and included infection, anastomotic leak, dehiscence, pain, postoperative ileus, dehydration and small bowel obstruction. In all trials reporting SAEs, the rate in the alvimopan group was equal to or less than in the placebo group, and no trials reported deaths attributed to alvimopan.

One study investigating 0.5 mg twice daily alvimopan for 12 months for the treatment of opioid-induced bowel dysfunction found a higher incidence of myocardial infarction in the alvimopan group. The events occurred 1-4 months after the start of treatment, and the increased risk of MI has not been observed in other studies with shorter duration (7 days) of alvimopan in postoperative patients. A large matched-cohort study using a national inpatient database including 7050 patients found a *lower* risk of cardiovascular morbidity in the alvimopan cohort than in the control cohort (19.4% vs. 24.0%,  $p = 0.0001$ ).

Alvimopan has been found to decrease the time to return of bowel function and time to discharge in multiple randomized controlled trials, as seen in the table below.

Study	Year	Procedures	Intervention	N	Endpoint(s) 
Taguchi et al. 	2001	15 LBR 63 TAH	Alv. 1 mg	26	Time to flatus: RR 1.2 (p=0.59) Time to BM: RR 1.2 (p=0.69) Time to D/C: RR 1.2 (p=0.48)
			Alv. 6 mg	26	Time to flatus: RR 2.5 (p=0.004) Time to BM: RR 2.9 (p=0.01) Time to D/C: RR 2.4 (p=0.003)
			Placebo	26	
Wolff et al. 	2004	395 LBR 56 SBR 18 TAH	Alv. 6 mg	155	Time to GI-3: HR 1.28 (p<0.05) Time to GI-2: HR 1.38 (p=0.013) Time to D/C: HR 1.25 (p=0.070)
			Alv. 12 mg	165	Time to GI-3: HR 1.54 (p<0.001) Time to GI-2: HR 1.67 (p<0.001) Time to D/C: HR 1.42 (p=0.003)
			Placebo	149	
Delaney et al. 	2005	303 LBR 129 TAH	Alv. 6 mg	150	Time to GI-3: HR 1.45 (p=0.003) Time to GI-2: HR 1.46 (p=0.007) Time to D/C: HR 1.50 (p<0.001)
			Alv. 12 mg	146	Time to GI-3: HR 1.28 (p=0.059) Time to GI-2: HR 1.31 (p=0.057) Time to D/C: HR 1.18 (p=0.17)
			Placebo	153	
Herzog et al. 	2006	519 TAH	Alv. 12 mg	413	Time to GI-3: HR 1.16 (p=0.176) Time to GI-2: HR 2.23 (p<0.001) Time to D/C: HR 1.13 (p=0.268)
			Placebo	106	
Viscusi et al. 	2006	437 LBR/SBR 200 TAH	Alv. 6 mg	220	Time to GI-3: HR 1.24 (p=0.037) Time to GI-2: HR 1.40 (p=0.005) Time to D/C: HR 1.36 (p=0.002)
			Alv. 12 mg	221	Time to GI-3: HR 1.26 (p=0.028) Time to GI-2: HR 1.36 (p=0.012) Time to D/C: HR 1.30 (p=0.010)
			Placebo	224	
Buchler et al. 	2008	705 LBR/SBR	Alv. 6 mg	237	Time to GI-3: 84.2 hrs (p=0.042) Time to GI-2: 95.2 hrs (p<0.001) Time to D/C: HR 1.08 (p=0.13)
			Alv. 12 mg	239	Time to GI-3: 87.8 hrs (p=0.20) Time to GI-2: 98.8 hrs (p=0.008) Time to D/C: HR 1.07 (p=0.49)
			Placebo	229	Time to GI-3: 92.6 hrs Time to GI-2: 109.5 hrs
Ludwig et al. 	2008	654 LBR/SBR	Alv. 12 mg	329	Time to GI-3: HR 1.5 (p<0.001) Time to GI-2: HR 1.5 (p<0.001) Time to D/C: HR 1.4 (p<0.001)
			Placebo	325	
Lee et al. 	2014	280 RC	Alv. 12 mg	143	Time to GI-2: HR 1.8 (p<0.0001) Time to D/C: HR 1.7 (p=0.0002)
			Placebo	137	
LBR, large bowel resection (colectomy); SBR, small bowel resection; TAH, total abdominal hysterectomy; Alv., alvimopan; GI-3, solid food + BM/flatus; GI-2, solid food + BM; RR, relative risk; BM, bowel movement; D/C, discharge; HR, hazard ratio; RC, radical cystectomy					
 Versus Placebo					
 adjusted for sex and surgical duration					

A meta-analysis incorporating the studies listed above has been completed. The pooled

analysis revealed a significant reduction in time to GI-2 bowel function (6 mg, HR = 1.5,  $p < 0.00001$ ; 12 mg, HR = 1.59,  $p < 0.00001$ ), BM (6 mg, HR = 1.54,  $p < 0.00001$ ; 12 mg, HR 1.74,  $p = 0.0002$ ), and time to discharge order written (6 mg, HR = 1.37,  $p < 0.00001$ ; 12 mg, HR = 1.34,  $p < 0.00001$ ) versus placebo.

From a pharmacokinetic standpoint, alvimopan is metabolized by the intestinal flora and is primarily excreted in the bile, secondarily in the feces, and 35% in the urine. Its half-life is 10-17 hours, although this is longer in patients with mild-moderate hepatic impairment (Child's Pugh Class A and B) and severe renal impairment. P450 drug-interactions...

Alvimopan is FDA-approved for short-term, in-hospital use in patients at risk for postoperative ileus, particularly those following bowel resection with primary anastomosis. However, due to potential increased cardiovascular risks with long-term use, distribution of the drug is restricted to short-term use (maximum 15 doses) under a Risk Evaluation and Mitigation Strategy (REMS), which includes only institutions enrolled in the ENTEREG Access Support and Education (E.A.S.E.) Program, of which UCSD is one. The current FDA-approved dose is 12 mg orally 30 minutes to 5 hours prior to surgery, followed by 12 mg orally twice daily beginning the day after surgery for up to seven days or until hospital discharge, with a maximum of 15 doses.

### **1.3 Rationale**

In an analysis of 50 consecutive CRS/HIPEC procedures performed at UCSD the median time to return of bowel function, as defined in prior phase III clinical trials with alvimopan (later of time to first bowel movement or tolerance of solid diet, GI-2), was 9 days. No studies have been published investigating the use of alvimopan after CRS/HIPEC. The current proposal is being performed to investigate the efficacy of alvimopan on the time to return of bowel function in patients undergoing CRS/HIPEC.

## **2.0 STUDY OBJECTIVES**

---

### **2.1 Primary Objective**

To determine the efficacy of alvimopan to reduce postoperative ileus in patients undergoing CRS/HIPEC, as measured by the composite of time to recovery of upper and lower GI function, as defined by the later of the following two events (GI-2):

- Time that the patient first tolerates solid food
- Time that the patient first passes a bowel movement

